10.11. Revision Surgery

It is recognized that during the course of the study, there is a possibility subjects may require a medical revision of the implant for events including but not limited to infection, erosion, and mechanical malfunction.

A medical revision is defined as a secondary surgery to modify or replace the initially implanted device. A replacement is a subset of medical revision, defined as removal of one or more components of the AMS 800 and/or implantation of a new component. Components include the cuff, pump, and PRB.

Any subject who receives a medical revision should return to the clinic for the next regular study visit as per his original schedule.

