11.1. Endpoints

11.1.1. Primary Endpoint

The primary endpoint is defined as treatment success based on the 24-hour pad-weight test. A 50% or greater reduction in pad-weight from baseline to 12 months post-device activation is considered a treatment success.

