11.1.1.1. Hypotheses

The study will evaluate whether the proportion of subjects experiencing a treatment success exceeds 65% at 12 months. The null and alternative hypotheses for this evaluation are

H₀: $p \le 65\%$ H₁: p > 65%

where p is the proportion of subjects who are a treatment success at 12 months.

11.1.1.2. Sample Size

The sample size calculation is based on an assumption that the treatment success rate is 80%⁴. With a one-sided type I error of 0.025 and a type II error of 0.10 (90% power), a sample size of 96 subjects are needed to demonstrate the proportion of subjects who are a treatment success exceeds 65%. Assuming a 20% attrition rate, at least 120 subjects with AMS 800 AUS procedure are required.

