11.1.1.3. Statistical Methods

The hypotheses will be evaluated using a one-sided exact binomial test. In addition, a two-sided 95% exact (Clopper-Pearson) confidence interval will be presented. Sensitivity analysis to missing data will be performed using tipping-point analysis. If a medical revision is performed due to efficacy reasons at or prior to the 12 month visit, then the subject is considered as experiencing a treatment failure.

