11.1.2.2.1 Statistical Methods

The proportion of subjects with a revision will be summarized by the Kaplan-Meier estimate at 3 months (90 days), 6 months (180 days) and 12 months (365 days) post device activation. The revision rate will be summarized by a revision reason, e.g. infection, erosion, and mechanical malfunction if applicable.

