20.2. Independent Medical Reviewer

An Independent Medical Reviewer (IMR) is an independent practitioner with trial relevant therapeutic expertise that reviews and adjudicates important endpoints and relevant adverse events reported by study investigators. The IMR will review a safety event dossier, which may include copies of subject source documents provided by study sites, for all reportable events, excluding device deficiencies. IMR responsibilities, qualifications, membership, and procedures are outlined in the IMR Charter.

21. Suspension or Termination

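### Only revisions for undefined efficacy reasons count as primary-endpoint failures, and no planned analysis shows the 12-month success rate with every revision counted as a failure

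*Combined protocol and SAP*

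**What the plan says.** The endpoint is set in section 11.1.1: "A 50% or greater reduction in pad-weight from baseline to 12 months post-device activation is considered a treatment success". Section 11.1.1.1 sets the goal: "The study will evaluate whether the proportion of subjects experiencing a treatment success exceeds 65% at 12 months".

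Section 11.1.1.3 adds one rule about repeat surgery. The subject is a failure "If a medical revision is performed due to efficacy reasons at or prior to the 12 month visit". The phrase is not explained there, in section 10.11, or in the definitions table (section 26.2), whose entry for medical revision points back to 10.11.

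Section 10.11 defines a revision broadly, as secondary surgery that modifies or replaces the implant. Its open list of causes names infection, erosion and mechanical malfunction. On timing it says: "Any subject who receives a medical revision should return to the clinic for the next regular study visit as per his original schedule". Under Table 10.1-1, all follow-up windows run from device activation.

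Revision is also a secondary endpoint, with Kaplan-Meier estimates at 3, 6 and 12 months. Section 11.1.2.2.1 adds: "The revision rate will be summarized by a revision reason, e.g. infection, erosion, and mechanical malfunction if applicable".

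Section 20.2 provides an Independent Medical Reviewer who "reviews and adjudicates important endpoints and relevant adverse events reported by study investigators". It does not mention the reason for a revision.

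**The concern.** The primary result will be read as the success rate of the implanted sphincter one year after activation. Under the rule as written, a man who needed a second operation for infection or erosion is judged on his Month 12 pad test alone. If a component was replaced at month 9 and the pads are light at month 12, he is a success with hardware that has been working for about three months. For malfunction the scoring is unclear: a sphincter that fails mechanically and lets the man leak again could be classed as a mechanical or an efficacy revision, and the plan does not say which.

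The goal may be decided by a handful of men, so the reader needs to see how many successes followed a revision. If the classification is settled only after pad weights are known, it can be challenged as driven by the outcome.

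**Working it through.** **1. The plan's own figure.** Inputs from section 11.1.1.2: null rate 0.65, assumed rate 0.80, one-sided alpha 0.025, 90% power, n = 96, 20% attrition.
- Smallest r with P(X ≥ r | 96, 0.65) ≤ 0.025 is r = 72 (75.0%), where P = 0.0236. At r = 71, P = 0.039.
- Power = P(X ≥ 72 | 96, 0.80) = 0.909.
- 96 / (1 − 0.20) = 120.

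The stated 96 and 120 reproduce. The issue is how the endpoint is scored.

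**2. Does any planned analysis cover revised men?**
- Tipping-point analysis (11.1.1.3, 11.2.1): missing data only. These men have observed pad weights.
- As Treated and Per Protocol (11.2): neither definition removes a man because of a revision.
- Revision summaries (11.1.2.2.1): not cross-tabulated with the primary outcome.
- Nothing in the plan sets aside post-revision pad weights or restarts the clock.

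**3. How many men?** No 12-month revision rate is given. The only figure is in section 4.1: 75% revision-free at 5 years, not split by reason. Assuming a constant hazard:
- Year-1 risk = 1 − 0.75^(1/5) = 0.0559, or 5.6%.
- 0.0559 × 96 = 5.4 men, all reasons combined.
- If 80% of them pass the pad test (assumption): 5.4 × 0.80 = 4.3 men.
- Efficacy revisions, already failures, would come off this number.

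**4. Effect on the decision at n = 96.** The planned rate gives 0.80 × 96 = 76.8, taken as 77.

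| Start | Recoded to failure | Result | One-sided p | Goal |
|---|---|---|---|---|
| 77/96 (80.2%) | 5 | 72/96 (75.0%) | 0.0236 | met |
| 77/96 (80.2%) | 6 | 71/96 (74.0%) | 0.039 | missed |
| 72/96 (75.0%) | 1 | 71/96 (74.0%) | 0.039 | missed |

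**5. Range of assumed revision rates.** Let f be the proportion revised for non-efficacy reasons, with 80% of them passing the test. Column A counts the affected men, 96 × 0.80f. Column B is the chance of meeting the goal when success with every revision as a failure is exactly 65%: P(X ≥ 72 | 96, 0.65 + 0.80f). Column C is the power of the stricter scoring if the planned 80% includes post-revision successes: P(X ≥ 72 | 96, 0.80 − 0.80f).

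| f | A | B | C |
|---|---|---|---|
| 2% | 1.5 | 0.048 | 0.826 |
| 5% | 3.8 | 0.122 | 0.643 |
| 8% | 6.1 | 0.255 | 0.430 |
| 10% | 7.7 | 0.378 | 0.299 |

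Column B is not a type I error under the plan's own definition of success. It measures how far the two readings of success can diverge.

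**The case against.** The strongest reply is that this is a legitimate choice of estimand. The plan has an explicit rule for revision, reports revision as its own endpoint by reason, and may intend to measure continence under AMS 800 treatment including repair. Scoring every revision as a failure would fold safety into efficacy. That stands, and it is why the main rule need not change. It does not answer the undefined term or the absence of any analysis linking the two endpoints.

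Four stronger readings are tempting but not supported:
- *Malfunction escapes the rule.* The lists of causes are open, and nothing excludes a malfunction with renewed leakage from the efficacy class. For malfunction the defect is ambiguity; infection and erosion are the clearer gaps.
- *The implanting site sets the label.* No section says so. Related infections and erosions are reportable (18.1) and go to the Independent Medical Reviewer (20.2), whose charter is not among the documents. What can be said is that the protocol does not tie the reviewer to this rule.
- *Success is on a second device.* A revision may modify the implant or replace a single component.
- *A man revised shortly before Month 12 must be tested before reactivation.* The visit is day 365 ± 3 months (10.9) and is not missed until the window closes (10.7). Early testing is possible but not forced, and no reactivation interval after revision is stated.

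**Conclusion.** The gap in the text is certain: the failure rule turns on an undefined term, and a man revised for infection or erosion who passes the pad test is scored a success with no planned analysis showing the effect. Whether it changes the conclusion is uncertain. Five of 96 is an upper guide, resting on a constant hazard, every revision being non-efficacy, and every revised man being evaluable and passing the test; about four applies if 80% pass. At the planned success rate, even five recodes leave the goal met. The rule becomes decisive if the observed count is near 72, or if early revisions are commoner than a constant hazard implies, which the documents neither support nor exclude. A reader might infer that the trial would probably miss its goal under stricter scoring; the figures do not show that. This is an inexpensive improvement worth making before analysis, not a flaw in the sample size or the test.

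**What to change.** Keep the main rule and make three additions:

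1. In section 11.1.1.3, pre-specify a sensitivity analysis of the primary endpoint in which any revision, component replacement or removal at or before the Month 12 visit, whatever the reason, is a failure. Report it beside the primary result, with the number of men recoded. Name removal expressly, because 10.11 counts removal alone as a replacement while 26.2 also requires a new component. Present it as an estimate with its confidence interval, not as a second test, since column C shows that its power may be well below 90%.
2. Define efficacy reasons for the analysis, including how a malfunction with return of leakage is scored.
3. Have the existing Independent Medical Reviewer classify each revision reason without sight of post-revision pad weights.

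Section 11.3.6 already allows an amended analysis plan before the analyses are run. The cost is some plan wording, one extra table and one line in the reviewer's charter. The sensitivity figure will be somewhat less favourable than the main one. Visit schedules, clinical management and sample size are unchanged.

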11.1.2. Secondary Endpoints

The secondary endpoints are explanatory in nature; descriptive statistics including 95% confidence intervals will be used to summarize all these endpoints unless specified otherwise.

11.1.2.1. Secondary Endpoint 1 – Serious Adverse Events

The endpoint is a serious adverse event.

11.1.2.1.1 Statistical Methods

Serious adverse events will be summarized using descriptive statistics (event counts, proportion of subjects with a serious adverse event), and by relatedness to procedure and/or

device. The serious adverse event rates will be summarized by the Kaplan-Meier estimate at 3 months (90 days), 6 months (180 days) and 12 months (365 days) post device activation.

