18.1. Reportable Events by investigational site to Boston Scientific

It is the responsibility of the investigator to assess and report the following events to BSC if they occurred from the time of index procedure through the end of the subject's participation in the study:

- Serious Adverse Events
- Serious Adverse Device Effects
- Adverse Device Effects
- Procedure Related Adverse Events
- Device Deficiencies

Events to be reported include both anticipated and expected post procedural events, in addition to any other unanticipated and unexpected events.

When possible, the medical diagnosis should be reported as the Event Term instead of individual symptoms.

If it is unclear whether or not an event fits one of the above categories, or if the event cannot be isolated from the device or procedure, it should be submitted as an adverse event and/or device deficiency.

Reportable events must be recorded in the eCRF. The Investigator or designee is responsible for updating the eCRF with new or updated information in relation to the already reported event as soon as he/she becomes aware.

Underlying diseases and chronic conditions are not reported as AEs unless there is an increase in severity or frequency during the course of the investigation. Death should not be recorded as an AE but should only be reflected as an outcome of one (1) specific SAE (see Table 18.2-1 for Safety definitions).

Refer to Instructions for Use for the known risks associated with the commercial device(s).

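### The Kaplan-Meier estimates for serious adverse events and revision are tied to device activation, which on the natural reading leaves out events between surgery and activation and gives never-activated men no time zero

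*Combined protocol and SAP*

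**What the plan says.** Section 11.1.2.1.1 plans two kinds of SAE summary. One is crude: "event counts, proportion of subjects with a serious adverse event", also by relatedness to procedure or device, with no time origin attached. The other is the "Kaplan-Meier estimate at 3 months (90 days), 6 months (180 days) and 12 months (365 days) post device activation".

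For revision, Section 11.1.2.2.1 begins "The proportion of subjects with a revision will be summarized by the Kaplan-Meier estimate at 3 months (90 days" and goes on to the same 180- and 365-day landmarks, again counted from activation. The only other revision summary is this: "The revision rate will be summarized by a revision reason, e.g. infection, erosion, and mechanical malfunction if applicable".

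Other sections set the frame:

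- Section 18.1 makes events reportable "if they occurred from the time of index procedure through the end of the" subject's participation.
- Section 11.2 analyses endpoints in ITT, which requires consent and a first incision but not activation. It adds an As Treated (AT) analysis for safety, with AT defined by successful implantation.
- Section 10.7 places activation about 4-6 weeks after surgery in its text. Its heading and Table 10.1-1 give 30-45 days.
- Section 10.11 states: "A medical revision is defined as a secondary surgery to modify or replace the initially implanted device".
- Section 11.1.2 adds: "The secondary endpoints are explanatory in nature".

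**The concern.** The safety objective covers events related to the procedure as well as to the device, and revisions for reasons such as infection and erosion. Either can occur before the device is switched on. If the curves start at activation, the immediate post-operative weeks are missing from the only safety summaries that carry stated 3-, 6- and 12-month landmarks. A reader would probably take the 12-month figure as the risk of having the operation, when it describes risk among activated men from activation onward.

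The population is also affected. ITT includes men whose implantation is not completed and men whose device is never activated. On an activation clock these men cannot be placed on the time axis, and the plan gives no rule for them. The AT analysis does not resolve this, because a man can be successfully implanted and still never be activated.

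**Working it through.** **The plan's own figures.** The documents state no expected SAE or revision rate, so there is none to reproduce. The number treated does reproduce: 96 / (1 - 0.20) = 120. It is used below only as an illustrative N.

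**Length of the gap.** Section 10.7's text gives 28-42 days; Table 10.1-1 gives 30-45 days. Together the range g is 28-45 days.

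**Position of the landmarks, in days from surgery (g + L).**

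| Landmark L after activation | Days from surgery | Share of first L days after surgery that precedes activation, g/L |
|---|---|---|
| 90 | 118-135 | 28/90 = 31% to 45/90 = 50% |
| 180 | 208-225 | 28/180 = 16% to 45/180 = 25% |
| 365 | 393-410 | 28/365 = 8% to 45/365 = 12% |

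Measured over the whole span from surgery to the last landmark, the gap is 28/393 = 7.1% to 45/410 = 11.0%. These are shares of time, not of risk.

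**Effect of omitting early events.** Let q be the risk of a first event before activation, r the later risk in men without an early event, and r' the later risk in men with one. Assume that all men are activated and none are censored.

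- Risk from surgery to the landmark: q + (1 - q)r.
- Activation-clock estimate: qr' + (1 - q)r.
- Difference: q(1 - r').

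For one man in 120 (q = 0.83%), the activation clock is lower by:

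- 0.83 points if r' = 0;
- 0.79 to 0.71 points if r' = 5% to 15%;
- 0.42 points if r' = 50%.

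For three men in 120 with r' = 5% to 15%, it is lower by 2.4 to 2.1 points. All values of r' are assumptions.

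**Worked counts (assumed; N = 120, no censoring, no later event in men with an early one).** The activation-clock range runs from every early-event man being activated to none of them being activated.

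| Early first events | Later first events | Activation clock | From surgery |
|---|---|---|---|
| 1 | 6 | 5.0% | 7/120 = 5.8% |
| 4 | 6 | 6/120 = 5.0% to 6/116 = 5.2% | 10/120 = 8.3% |
| 4 | 12 | 12/120 = 10.0% to 12/116 = 10.3% | 16/120 = 13.3% |

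**Effect of omitting never-activated men.** This has no fixed direction. Suppose 5 men are never implanted and stay event-free, and 12 of the others have a first event after activation. The activation clock gives 12/115 = 10.4%, against 12/120 = 10.0% in ITT, so the estimate rises. In the last table row, if the four early-event men are never activated, it falls from 13.3% to 10.3%.

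**Follow-up support for a procedure clock.** Assume 12-month visits spread evenly over 275-455 days after activation (three months taken as 90 days) and no other loss. The share still at risk at day 365 from surgery is (455 - (365 - g))/180, which is 66% for g = 28 and 75% for g = 45. At day 365 from activation it is (455 - 365)/180 = 50%. Attrition, which the plan allows for at 20%, would lower both.

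**The case against.** The strongest reply is that the two sections fix when the curve is read, not where it starts. An analyst could begin at incision, or enter early events at time zero. That is fair as far as it goes: the activation origin is implied, and a reader should not infer that the plan has a stated rule excluding early events. But the plan adopts neither alternative, and the choices give different numbers. Because the interval to activation varies between men, day 90 after activation is not a single point on a curve drawn from incision.

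A reader might also infer that early events are lost from the study. They are not. SAEs are collected from the index procedure and appear in the crude counts, proportions and relatedness tables. Early revisions could appear in the by-reason summary, though no separate crude count is specified.

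A sharper inference is that a man whose device is removed before activation and not replaced loses both his event and his place in the curve. The documents do not settle whether he has had a revision. Section 10.11 says "A replacement is a subset of medical revision, defined as removal of one or more components of the AMS 800" and joins this to implanting a new component with *and/or*; the glossary in Section 26.2 uses *and*. The passages must be reconciled, and the point does not depend on this case.

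Activation-based landmarks do match the visit schedule, which is a good reason to keep them as supplementary figures. The endpoints are also descriptive, which limits the consequence but does not remove the need for a defined origin and risk set.

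**Conclusion.** The point holds on the natural reading of both sections. The Kaplan-Meier estimates leave out first SAEs and revisions in the roughly 28-45 days before activation, and ITT men never activated have no time zero. Omitting early events understates cumulative risk from surgery. It does not follow that the net error must be downward, because excluding never-activated, event-free men works the other way.

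The size is unknown. Under the assumptions shown, each man in 120 with an early first event costs about 0.4 to 0.8 percentage points. Nor should the 31-50% share of the first 90 days be taken as a share of events.

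Revision is more exposed than SAEs, because its only planned summaries are the Kaplan-Meier estimate and the by-reason summary. No hypothesis test, and neither the primary endpoint nor the sample size, is affected. It should be fixed before analysis, as a matter of correct safety reporting.

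**What to change.** In Sections 11.1.2.1.1 and 11.1.2.2.1:

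1. Start the Kaplan-Meier clock at the index procedure in the ITT population and count events from first incision. Keep AT as the additional safety analysis already planned. Section 11.2 (successful implantation) and Section 26.2 (attempted implantation) define AT differently and need reconciling.
2. Censor at study exit or last contact, and state that this includes men never activated.
3. Report at 90, 180 and 365 days from the procedure, with the number at risk at each.
4. Keep the activation-based estimates as labelled supplementary figures. Day 365 from surgery stops 28-45 days short of the planned post-activation year, so both are needed.
5. Add crude SAE and revision counts split into procedure to activation and after activation.
6. Reconcile Sections 10.11 and 26.2 on removal without a new component.

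**Cost.** Section 11.3.6 allows the change through an amended SAP approved before the analyses. Changing protocol text needs ethics review under Section 15.3. No new data are required: Section 15.5 lists procedure and adverse event dates, and either clock needs the revision date. The main safety landmarks would no longer coincide with the activation-based visits. The two sets of estimates cover different spans (days 0-90 from surgery, against a span from about day 28-45 to day 118-135, for the first landmark), so they must be labelled and not read as one quantity.

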11.1.2.2. Secondary Endpoint 2 - Revision

The endpoint is a medical revision of the implant for events including but not limited to infection, erosion, and mechanical malfunction.

11.1.2.2.1 Statistical Methods

The proportion of subjects with a revision will be summarized by the Kaplan-Meier estimate at 3 months (90 days), 6 months (180 days) and 12 months (365 days) post device activation. The revision rate will be summarized by a revision reason, e.g. infection, erosion, and mechanical malfunction if applicable.

11.1.2.3. Secondary Endpoint 3 – 50% Reduction in pad weight

The endpoint is the proportion of subjects with at least 50% reduction from baseline in urinary incontinence as measured by 24-hour pad weight test at device activation, and 6 months post device activation.

